9.1 Early Stopping

In the event that the study is stopped early and only a reduced amount of outputs are needed, safety data will only be reported for the period beginning with the first dose of active IMP in this study. Only incidence and number of events will be presented for the following categories:

- TEAEs
- Serious TEAEs

Data will be presented as collected, no imputations or data exclusion will be made.

The list of outputs produced in the case the study is stopped early are provided in 16Appendix 1: List of Tables, Figures and Listings.

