9.2 Primary Estimand of the Primary Objective

Safety data will be reported for two periods:

- The period beginning with the first dose of active IMP in this study
- The period beginning with the first dose of active IMP across this study and the parent study

The primary safety endpoints will be the incidence and rate per 100 patient-years for:

- TEAEs
- TEAEs of Grade 2 or above
- TEAEs of Grade 3 or above
- Serious TEAEs
- Fatal TEAEs
- TEAEs causing discontinuation of study drug
- Study drug related TEAEs (defined by an investigator assessment of possible, probable, or definite relationship to IMP)
- Study drug related TEAEs of Grade 2 or above
- Study drug related TEAEs of Grade 3 or above
- Study drug related serious TEAEs
- Study drug related fatal TEAEs
- Study drug related TEAEs causing discontinuation of study drug

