9.2.2 Analytical Approach

The endpoints described for the primary safety analysis will be summarised in the overall summary of adverse events table with a row for each endpoint. The number and percentage of patients with each TEAE, the total number of events and the rate per 100 patient-years will be presented for each treatment group.

Other adverse events summaries considered as secondary safety endpoints are further described in [Section 11.2](#).

10 Efficacy Analyses

All efficacy estimands will use the FAS or the parent study specific FAS for the study/cohort specific analysis.

Treatment condition: planned treatment will be considered.

Descriptive statistics will be provided to summarize all efficacy endpoints using the grouping specified in Section 8 which considers treatment groups in this study and the parent study.

All efficacy data will be listed, including both individual item scores and calculated questionnaire summary scores.

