V4.0	Removed endpoints for worst-case change from baseline with respect to values outside the normal ranges for vital signs and ECG parameters	Worst-case change from baseline with respect to values outside the normal ranges for vital signs, ECG parameters and clinical laboratory parameters for given as secondary safety endpoint but only changes with respect to normal ranges were summarized for the lab parameters. For ECG and vital signs, it was felt that only changes from PCI criteria were of specific interest.
V4.0	Efficacy outputs will not be produced as planned	The study was early terminated after the parent study primary endpoint was not met.
V4.0	Only reduced amount of disposition, demography and safety data will be summarised and listed	The study was early terminated after the parent study primary endpoint was not met.

15 Bibliography

16 Appendix 1: List of Tables, Figures and Listings

All outputs detailed in the following sections will be produced for the final analysis. In addition, those which will be produced for the interim analysis are flagged in the 'Interim' column.

If the study is stopped early, outputs will be produced as specified in the Early Stop column.

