16.1 Study Population

If the study is stopped early, study population outputs will be produced as planned originally.

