16.3 Safety

If the study is stopped early, safety outputs will be produced as planned originally.

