16.3.1 Tables

Number	Title	Population	Data Point Set	Early Stop	Programming notes for Early Stop
14.3.1.1.1	Overview of TEAEs reported in 208	FAS	DPS1	Yes	New number 14.3.1.1
14.3.1.1.2	Overview of TEAEs reported since first active dose in 207 or 208	FAS	DPS2	No	

Number	Title	Population	Data Point Set	Early Stop	Programming notes for Early Stop
14.3.1.2.1	Summary of the Incidence and Rate per 100 Patient-Years of TEAEs by System Organ Class and Preferred Term	FAS	DPS1	Yes	New number 14.3.1.2 Only present E (number of events); exclude rate
14.3.1.2.2	Summary of the Incidence and Rate per 100 Patient-Years of TEAEs by System Organ Class and Preferred Term	FAS	DPS2	No	
14.3.1.3.1	Summary of the Incidence and Rate per 100 Patient-Years of TEAEs of Grade 2 or Above by System Organ Class and Preferred Term	FAS	DPS1	No	
14.3.1.3.2	Summary of the Incidence and Rate per 100 Patient-Years of TEAEs of Grade 2 or Above by System Organ Class and Preferred Term	FAS	DPS2	No	
14.3.1.4.1	Summary of the Incidence and Rate per 100 Patient-Years of TEAEs of Grade 3 or Above by System Organ Class and Preferred Term	FAS	DPS1	No	
14.3.1.4.2	Summary of the Incidence and Rate per 100 Patient-Years of TEAEs of Grade 3 or Above by System Organ Class and Preferred Term	FAS	DPS2	No	
14.3.1.5.1	Summary of the Incidence and Rate per 100 Patient-Years of Serious TEAEs by System Organ Class and Preferred Term	FAS	DPS1	Yes	New number 14.3.1.4 Only present E (number of events); exclude rate
14.3.1.5.2	Summary of the Incidence and Rate per 100 Patient-Years of Serious TEAEs by System Organ Class and Preferred Term	FAS	DPS2	No	

Number	Title	Population	Data Point Set	Early Stop	Programming notes for Early Stop
14.3.1.6.1	Summary of the Incidence and Rate per 100 Patient-Years of Fatal TEAEs by System Organ Class and Preferred Term	FAS	DPS1	No	
14.3.1.6.2	Summary of the Incidence and Rate per 100 Patient-Years of Fatal TEAEs by System Organ Class and Preferred Term	FAS	DPS2	No	
14.3.1.7.1	Summary of the Incidence and Rate per 100 Patient-Years of TEAEs Causing Discontinuation of Study Drug by System Organ Class and Preferred Term	FAS	DPS1	No	
14.3.1.7.2	Summary of the Incidence and Rate per 100 Patient-Years of TEAEs Causing Discontinuation of Study Drug by System Organ Class and Preferred Term	FAS	DPS2	No	
14.3.1.8.1	Summary of the Incidence and Rate per 100 Patient-Years of Study Drug Related TEAEs by System Organ Class and Preferred Term	FAS	DPS1	No	

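### With the study stopped early, SAP 9.1 drops the rate and 10 of the 12 primary TEAE categories, and Appendix 1 keeps the overview table without aligning it to that limit

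*SAP*

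**What the plan says.** **Full plan.** SAP 9.2 states: "The primary safety endpoints will be the incidence and rate per 100 patient-years for" a list of 12 TEAE categories. SAP 9.2.2 says that these endpoints "will be summarised in the overall summary of adverse events table with a row for each endpoint". That table gives the number and percentage of patients, the number of events and the rate, by treatment group.

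**Early-stop text.** SAP 9.1 applies if the study stops early and a reduced set of outputs is needed. It restricts reporting to the period from first dose in study 208 and adds: "Only incidence and number of events will be presented for the following categories". Two categories follow, TEAEs and serious TEAEs. For the list of outputs it points to Appendix 1. SAP 11.1 adds one summary of non-serious TEAEs.

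**Status.** SAP Section 14 (Table 9) records that the study was terminated early, after the parent study missed its primary endpoint, and that a reduced set of disposition, demography and safety outputs will be produced.

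**Appendix 1.** Its opening text gives the rule: "If the study is stopped early, outputs will be produced as specified in the Early Stop column". In 16.3.1 the table titled "Overview of TEAEs reported in 208" (14.3.1.1.1, DPS1) is flagged Yes, and its only programming note is a new table number. The other three tables flagged Yes (14.3.1.2.1, 14.3.1.5.1 and 14.3.1.14.1) carry the note "Only present E (number of events); exclude rate". The lead-in to 16.3 reads: "If the study is stopped early, safety outputs will be produced as planned originally". The lead-in to 16.1 reads: "If the study is stopped early, study population outputs will be produced as planned originally".

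**The concern.** Safety is the primary objective, and the overview table is where the plan puts the primary endpoint. Under SAP 9.1 that endpoint loses its rate and most of its categories. The lost categories include those a safety reader looks for first: Grade 3 or above, drug-related, and causing discontinuation.

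The rate matters more in a study cut short than in one that runs to plan. Participants stop at different times, so percentages and counts mix event frequency with length of observation.

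The plan also does not carry the limit through to the table specification. Someone programming from Appendix 1 sees three tables told to omit the rate, one table with no such instruction, and a lead-in saying that nothing changes.

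**Working it through.** The plan gives no figure to reproduce. The check is a count of categories and flags, plus two small calculations.

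1. **Primary categories.** SAP 9.2 lists 12. SAP 9.1 names 2. Not named: 12 − 2 = 10. Of the two statistics in the endpoint, 9.1 keeps incidence (and adds number of events) and omits the rate.

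2. **Safety tables, SAP 16.3.1.** There are 14 AE topics × 2 data point sets = 28, plus 6 laboratory, 2 ECG and 2 vital-sign tables, giving 28 + 10 = 38. Flagged Yes: 14.3.1.1.1, 14.3.1.2.1, 14.3.1.5.1 and 14.3.1.14.1. Flagged No: 38 − 4 = 34.

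3. **Study-population tables, SAP 16.1.1.** 7 + 2 + 2 + 5 + 3 = 19. Flagged Yes: 14.1.1.1, 14.1.1.3, 14.1.2.1 and 14.1.7. Flagged No: 19 − 4 = 15.

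4. **Where else the 10 categories could appear.** The DPS1 tables by system organ class and preferred term for the 12 categories are 14.3.1.2.1 to 14.3.1.13.1. Only 14.3.1.2.1 and 14.3.1.5.1 are Yes, so 10 are No. The overview is therefore the only kept table that could summarise those 10 categories separately. Limited to what 9.1 names, it would largely repeat the totals of two other kept tables. Fatal events would still be counted within serious TEAEs, because death is a seriousness criterion in protocol 9.3. The general AE listing (16.2.7.1.1) is kept; the separate serious, fatal and discontinuation listings are not.

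5. **Why counts alone are hard to read (illustration).** The documents give no exposure by group at termination. SAP 11.2 uses exposure cut-offs from 28 to 252 days. With the SAP's 30-day TEAE window and full follow-up, observation runs from 28 + 30 = 58 to 252 + 30 = 282 days. At the same constant event rate, expected events per participant differ by 282/58 = 4.9-fold between those extremes.

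6. **Separate, minor: the window for a rate.** SAP 5.3.4.2, 11.3 and Table 9 use 30 days after last dose. Protocol 9.5.5 does not record new AEs starting more than 28 days after it. If events stop at day 28 and patient-time runs to day 30, a constant rate is understated by 1 − (d + 28)/(d + 30), where d is days of exposure:

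| d (days) | Calculation | Understatement |
|---|---|---|
| 28 | 1 − 56/58 | 3.4% |
| 84 | 1 − 112/114 | 1.8% |
| 168 | 1 − 196/198 | 1.0% |
| 252 | 1 − 280/282 | 0.7% |

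These are upper bounds at each duration, because protocol 9.4 has serious AEs reported to day 30.

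**The case against.** The strongest reply is that nothing is undecided. SAP 9.1 sits in the primary safety section and states exactly what is shown on early stopping. A specific early-stop rule overrides 9.2.2, which describes the full study, and the missing note on 14.3.1.1.1 is an omitted cross-reference. The study is descriptive and open-label, and it has ended. The AE listing is kept, grade, seriousness, causality and action taken are recorded for each event, and exposure table 14.1.7 is kept.

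Most of this stands. A reader might infer that the primary table has no defined content. The documents do not support that, because 9.1 defines it. What remains is that Appendix 1 restricts three tables explicitly and not this one, and that 11.1 refers back to the primary safety endpoints without saying whether it means two categories or twelve. That justifies a clarifying note. The reply also does not touch the main point: following 9.1 as written discards most of the primary summary when a table that could hold it is already being produced.

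Other stronger readings also fail:

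- **All 38 safety tables are due.** The opening of Appendix 1 makes the Early Stop column the rule, so the lead-ins in 16.1 and 16.3 are leftover wording.
- **The note on the three tables removes incidence.** Their titles, 9.1 and the 5% threshold in 11.1 all keep it; the note chooses events over rate.
- **The combined 207/208 primary endpoint was dropped silently.** SAP 9.1, 11.1 and the flags drop it openly.
- **The defect can be sized by using dosing days as the denominator.** The SAP assigns no denominator to the TEAE rate, and 9.1 would not present that rate.

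**Conclusion.** The point holds as a cheap improvement together with an alignment error. If 9.1 is followed, which is the more natural reading, the rate per 100 patient-years and 10 of 12 primary categories are not summarised. TEAEs of Grade 3 or above, drug-related TEAEs and TEAEs causing discontinuation are then recoverable only from the AE listing. A reader could form an approximate rate for the two kept categories from the exposure table, but for no others without counting from the listing.

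Table 9 mentions a reduced amount of safety output but names neither the rate nor the categories. The lead-ins in 16.1 and 16.3 contradict the flags (15 of 19 and 34 of 38 tables No) and are editorial slips.

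No data are lost and no inference is affected. The counts are certain; that 9.1 controls the overview is a judgement from its place and wording. The 28/30-day mismatch is separate and small, at most about 3.4% at 4 weeks of exposure and less with longer exposure. It assumes a constant event rate.

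**What to change.** 1. Amend SAP 9.1 and add a programming note so that kept table 14.3.1.1.1 (DPS1) shows all 12 primary categories with n, %, number of events, patient-years and rate per 100 patient-years.
2. Define patient-years over the window in which TEAEs are counted: from first dose in study 208 to the earlier of the end of the TEAE window and the end of study.
3. If the sponsor prefers to keep the 9.1 limit, write it into the note on 14.3.1.1.1 and name the dropped rate and the 10 dropped categories in Table 9, with the reason.
4. Either way, replace the lead-in sentences in 16.1 and 16.3 with a reference to the Early Stop column.
5. Separately, reconcile the 30-day window in the SAP (5.3.4.2, 11.3, Table 9) with the recording limit in protocol 9.5.5.

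Cost: SAP wording, programming notes, a few more rows in a table already being produced and one derived variable. No new data and no new table.

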9.2 Primary Estimand of the Primary Objective

Safety data will be reported for two periods:

- The period beginning with the first dose of active IMP in this study
- The period beginning with the first dose of active IMP across this study and the parent study

The primary safety endpoints will be the incidence and rate per 100 patient-years for:

- TEAEs
- TEAEs of Grade 2 or above
- TEAEs of Grade 3 or above
- Serious TEAEs
- Fatal TEAEs
- TEAEs causing discontinuation of study drug
- Study drug related TEAEs (defined by an investigator assessment of possible, probable, or definite relationship to IMP)
- Study drug related TEAEs of Grade 2 or above
- Study drug related TEAEs of Grade 3 or above
- Study drug related serious TEAEs
- Study drug related fatal TEAEs
- Study drug related TEAEs causing discontinuation of study drug

9.2.1 Estimands

The primary safety estimands will use the FAS or the parent study specific FAS for the study/cohort specific analysis.

Treatment condition: actual treatment received will be considered.

Population summary measure of interest:

- For the endpoints looking at the period defined by this study only - the incidence and rate per 100 patient-years of each category of TEAEs (DPS1)
- For the endpoints looking at the period defined since first dose of the active IMP in this study and the relevant parent study - the rate per 100 patient-years of each category of TEAEs by treatment group (DPS2)

Intercurrent events will be accounted for in the following manner:

Table 1: Intercurrent Event Strategies of the Primary Estimand

Discontinuation of treatment	The use of prohibited medications or TCS/TCI rescue therapy, non-compliance with study drug, and any deviations from protocol
Composite strategy Only events which start within 30 days after discontinuation of treatment (TEAEs) will be included in the assessments of incidences and rates	Treatment policy strategy: Data will be used as collected

9.2.2 Analytical Approach

The endpoints described for the primary safety analysis will be summarised in the overall summary of adverse events table with a row for each endpoint. The number and percentage of patients with each TEAE, the total number of events and the rate per 100 patient-years will be presented for each treatment group.

Other adverse events summaries considered as secondary safety endpoints are further described in [Section 11.2](#).

10 Efficacy Analyses

All efficacy estimands will use the FAS or the parent study specific FAS for the study/cohort specific analysis.

Treatment condition: planned treatment will be considered.

Descriptive statistics will be provided to summarize all efficacy endpoints using the grouping specified in Section 8 which considers treatment groups in this study and the parent study.

All efficacy data will be listed, including both individual item scores and calculated questionnaire summary scores.

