11.1. General Statistical Considerations

Statistical analysis will be performed using SAS software Version 9.3 or later.

Continuous variables will be summarized using the mean, standard deviation, median, minimum value, and maximum value. Categorical variables will be summarized using frequency counts and percentages.

No inferential statistical testing will be performed. Data will be displayed using summary statistics together with 95% confidence intervals where applicable.

Descriptive statistics will also be used extensively in figures to visualize the data. These include but are not limited to mean (SE) plots against time, waterfall plots for individual changes at a specific time point, vertical bar plots showing percentages of participants meeting a specific criterion, scatter plots to look at correlations between endpoints or timepoints.

Data will be listed in data listings.

Baseline will be defined as the baseline value taken from the parent study. In some cases, change prior to first dose of EDP1815 and change since first dose in this study may also be analyzed.

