11.4. Planned Analyses

All analyses will be descriptive in nature and no inferential statistics will be performed. 95% confidence intervals of mean changes and incidences or rates may be displayed where appropriate.

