11.7.3 Physical Examination

All clinically significant abnormalities identified through physical examination should be recorded as adverse events and listed with adverse events. No separate listings of physical examinations will be produced.

12 Reporting Conventions

When reporting relative frequencies or other percentage values, the following rules apply:

- For values where all subjects fulfil certain criteria, the percentage value will be displayed as 100
- For values where the absolute frequency is 0, there will be no percentage presented at all
- All other percentage displays will use 1 decimal place

When reporting descriptive statistics, the following rules will apply in general:

- n will be an integer
- Mean and median will use 1 decimal place more than the original data
- Standard deviation will use 2 decimal places more than then original data
- Minimum and maximum will be reported using the same number of decimal places as the original value
- If no subjects have data at a given timepoint, for example, then only n=0 will be presented. However, if n<3, present the n, min and maximum only. If n=3, n, mean, median, minimum and maximum will be presented only. The other descriptive statistics will be left blank

13 Technical Details

Statistical evaluation will be performed by [REDACTED]

The datasets for the interim and final analyses will follow analysis dataset model (ADaM) data specifications and will used standard data tabulation model (SDTM) data sets provided by [REDACTED] data management as the source data.

All analyses will be performed using SAS version 9.4 or higher (SAS Institute, Cary, NC, USA).

14 Summary of Changes from the Protocol

The SAP is based on the latest Protocol v4.0.

Table 9: Summary of Changes from the Protocol

Protocol Version	Summary of Change	Justification for change
V4.0	DPS5 Added which consists of all data collected following the first dose of IMP in this study	Added the DPS5 for use in the listings
V4.0	DPS1 and DPS2 will consider 30-days period instead of 28-days The same applies to the TEAE definition where 30-days period after the last dose of treatment is considered.	Serious AEs are reported if they occur within 30 days of last dose so only summarising TEAEs up to 28 days doesn't seem adequate.
V4.0	DPS3, 3a, 3b are removed	The results for DPS3, DPS3a and DPS3b will be a subset of the results for DPS4, DPS4a and DPS4b, so these summaries are not needed

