14.2.9.5.1	Histogram of Number of Topical Tacrolimus, Pimecrolimus or Grade VII Corticosteroid Periods	FAS	DPS4	No	
14.2.9.6.1	Proportion of Participants Achieving Requirement for Topical Tacrolimus, Pimecrolimus or Grade VII Corticosteroid Over Time	FAS	DPS4	No	
14.2.9.7.1	Histogram of Number of Moderate Potency Topical Steroids Periods	FAS	DPS4	No	
14.2.9.8.1	Proportion of Participants Achieving Requirement for Moderate Potency Topical Steroids Over Time	FAS	DPS4	No	
14.2.10.1.1	Cumulative Incidence (+/- 95% CI) of Participants Achieving EASI-50	FAS	DPS4b	No	
14.2.10.2.1	Cumulative Incidence (+/- 95% CI) of Participants Achieving Sustained EASI-50	FAS	DPS4b	No	
14.2.11.1.1	Waterfall Plot of Change from Baseline in ADCT Score	FAS	DPS4	No	

Number	Title	Population	Data Point Set	Early Stop	Programming notes for Early Stop
14.2.11.2.1	Mean (+/-SD) Change from Baseline in ADCT Score Over Time	FAS	DPS4	No	
14.2.12.1.1	Waterfall Plot of Percentage Change from Baseline in EASI Score by Region	FAS	DPS4	No	
14.2.12.2.1	Mean (+/-SD) Percentage Change from Baseline in EASI Score Over Time by Region	FAS	DPS4	No	
14.2.12.3.1	Waterfall Plot of Change from Baseline in EASI Score by Region	FAS	DPS4	No	
14.2.12.4.1	Mean (+/-SD) Change from Baseline in EASI Score Over Time by Region	FAS	DPS4	No	
14.2.12.5.1	Proportion of Participants Achieving 50% Reduction in EASI Score Over Time by Region	FAS	DPS4b	No	
14.2.13.5.1	Change in Response States	FAS	DPS4b	No	

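### The SAP plans no 95% confidence interval for the primary TEAE incidence or rate, although the protocol foresees intervals where appropriate, and does not record or explain leaving them out

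*SAP*

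**What the plan says.** **Protocol.** Section 11.1 rules out inferential testing and then says: "Data will be displayed using summary statistics together with 95% confidence intervals where applicable". Section 11.4 repeats that all analyses are descriptive and adds: "95% confidence intervals of mean changes and incidences or rates may be displayed where appropriate". The protocol therefore treats intervals as part of descriptive reporting and names incidences and rates among the candidates.

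**SAP, full plan.** Section 9.2.2 puts the primary endpoints in one overview table, one row per endpoint. Each row gives the number and percentage of patients with the event, and "the total number of events and the rate per 100 patient-years will be presented for each treatment group". Sections 8, 11.3 and 12 add no interval for adverse events. The only intervals in the output list are on two exploratory efficacy figures in 16.2.2: "Cumulative Incidence (+/- 95% CI) of Participants Achieving EASI-50" and its sustained-response counterpart. Both are marked as not produced at early stop.

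**SAP, early stop.** Table 9 in Section 14 records: "The study was early terminated after the parent study primary endpoint was not met". Section 9.1 then applies: "Only incidence and number of events will be presented for the following categories", the categories being TEAEs and serious TEAEs. In 16.3.1 the retained tables by system organ class and preferred term carry the note "Only present E (number of events); exclude rate". The retained overview table, 14.3.1.1.1, carries no such note.

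**SAP, zero counts.** Section 12: "For values where the absolute frequency is 0, there will be no percentage presented at all".

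**The concern.** Safety is the sole primary objective, so the primary result is a set of incidences and rates. Their size depends on the data, and how much they can exclude depends on the number of participants and the exposure. Neither was planned: Protocol 11.8 and SAP Section 6 leave the sample size to roll-over from the parent study, and the study then ended early. The reader cannot know the precision beforehand and, as the SAP stands, is not shown it afterwards.

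This matters most for the rare categories. A zero in the serious TEAE row would appear without a percentage and without an upper limit, although zero in 20 participants and zero in 200 exclude very different true incidences. An exploratory EASI-50 curve was given an interval in the full plan, while the primary safety endpoint was not.

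**Working it through.** **1. Is an interval planned or its absence explained?**

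- Protocol 11.1: intervals accompany summary statistics where applicable.
- Protocol 11.4: intervals for incidences or rates are optional, where appropriate.
- SAP 9.2.2, 9.1, 11.3, 8 and 12: none for TEAEs, and no method named.
- SAP Table 9: lists changes as minor as renaming an intercurrent-event strategy, but has no entry on intervals.

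The SAP neither says where intervals are applicable nor gives a reason for having none.

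**2. What would an interval for incidence show?** The documents give no group size, expected count or interval, so there is no plan figure to reproduce. Group sizes of 20 to 300 are assumed for illustration.

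For 0 participants with an event out of n, the two-sided exact (Clopper-Pearson) 95% upper limit is 1 − 0.025^(1/n).

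| Assumed n | Upper limit, 0 affected |
|---|---|
| 20 | 1 − 0.025^(1/20) = 16.8% |
| 50 | 1 − 0.025^(1/50) = 7.1% |
| 100 | 1 − 0.025^(1/100) = 3.6% |
| 200 | 1 − 0.025^(1/200) = 1.8% |
| 300 | 1 − 0.025^(1/300) = 1.2% |

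For 1 participant in 50 (2.0%) the exact 95% interval is 0.05% to 10.65%.

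The chance of seeing no affected participant when the true incidence is 1% is 0.99^n: 0.61 for n = 50 and 0.37 for n = 100.

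**3. What would an interval for the rate show?** With zero events in T patient-years, the exact Poisson 95% upper limit is 100 × [χ²(0.975; 2 df)/2]/T = 100 × 3.69/T per 100 patient-years. T is n × weeks × 7/365.25. The 40 weeks are the planned maximum (36 treatment + 4 follow-up). The 12 weeks are an assumed truncated case, because the follow-up actually reached is not stated.

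| Assumed n | T at 40 weeks | Upper limit | T at 12 weeks | Upper limit |
|---|---|---|---|---|
| 20 | 15.3 | 24.1 | 4.6 | 80.2 |
| 50 | 38.3 | 9.6 | 11.5 | 32.1 |
| 100 | 76.7 | 4.8 | 23.0 | 16.0 |
| 200 | 153.3 | 2.4 | 46.0 | 8.0 |
| 300 | 230.0 | 1.6 | 69.0 | 5.3 |

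**4. Does the Poisson interval suit non-zero rates?** Not in general. SAP 11.3 counts every event in the rate, so one participant can contribute several. If events cluster within participants, the variance exceeds the Poisson variance and the exact Poisson interval is too narrow. The incidence interval is unaffected, because each participant counts once.

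**5. Which text governs the truncated study?** SAP 9.1 leaves incidence and event counts for two categories and no rate. Appendix 1 keeps overview table 14.3.1.1.1 without dropping the rate or restricting the rows, and the sentence opening 16.3 says safety outputs stay as planned. The incidence interval applies under either reading. A rate interval applies only if the rate is kept.

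**The case against.** The strongest reply is that nothing in the protocol has been broken. The general sentence in 11.1 is conditional, and the sentence in 11.4 that names incidences and rates is permissive. Leaving an option unused is not clearly a change that Table 9 must list. This stands, and a reader who infers a protocol breach goes further than the wording allows.

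Other tempting readings also lack support:

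- **That the study was small, that enrolment was cut short, or that only a handful of events per group was expected.** No sample size, enrolment figure or expected count is given. Table 9 says only that the study was terminated early.
- **That a zero will be taken as evidence of safety.** Neither document says so. It is a risk of the display, not a stated interpretation.
- **That dose columns cannot be compared.** The analyses are descriptive and only parent Cohort 3 is randomised between doses, so comparison is not an aim.
- **That fatal and Grade 3 or above rows are certainly affected in the truncated output.** Section 9.1 keeps only TEAEs and serious TEAEs.

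It is also fair to say that a reader can derive an exact incidence interval from the count and the group size, and that the exposure table (14.1.7) is kept at early stop. That reduces the loss but does not remove it: a primary result should carry its own statement of precision. A rate interval for recurrent events cannot be rebuilt from the totals.

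**Conclusion.** The point holds as an unexplained omission. The protocol foresees intervals as part of descriptive reporting. The SAP plans none for the primary TEAE incidence or rate, names no method and gives no reason.

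The size of the consequence depends on group sizes that the documents do not state. Over assumed sizes of 20 to 200, a bare zero is compatible with a true incidence of up to 16.8% down to 1.8%. No estimate is biased and no test is affected; what is missing is the statement of what the data can exclude. It is a cheap improvement that should be made, not a fault that invalidates the analysis.

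**What to change.** - **Incidence.** In SAP 9.2.2 and 9.1, add an exact (Clopper-Pearson) 95% interval for each incidence shown in overview table 14.3.1.1.1, by dose group and Total. Print the upper limit for zero counts too, as an exception to the Section 12 display rule.
- **Rate.** Wherever a rate per 100 patient-years is shown, add a 95% interval by a method that allows for repeat events within a participant, such as a robust variance or a bootstrap over participants. With zero events those methods give no usable limit, so use the exact Poisson upper limit there.
- **Consistency.** Reconcile SAP 9.1 with Appendix 1 on whether table 14.3.1.1.1 keeps the rate, and which rows it keeps, at early stop.
- **No testing.** Add no tests and no between-group comparisons.
- **If intervals are still not wanted.** Record and justify that in Table 9.

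The incidence intervals need only the counts and group sizes already in the table. The rate intervals need participant-level event counts and exposure. The cost is extra columns for each dose group and Total, some programming for the rate interval, and safety figures that look less certain.
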